9.1 Reporting and Documentation of Adverse Events

9.1.1 Reporting

At each visit, any AE directly observed or mentioned by the subject will be reported by the Investigator or designee on the page "Adverse Events" of the CRF (also called the "AE page"). The unmasked team will report AEs commencing at Visits 3 and 4 and the masked team will document AEs commencing at all other visits. The unmasked team will enter

eye-related AEs identified at Visits 3 and 4 into the CRF in a masked way and will perform focused follow up at subsequent visits of ocular AEs commencing at Visit 3 and Visit 4 until AE resolution or the determination that no further clinical evolution will occur. The following items must be documented:

Nature of the event with self-explanatory and concise medical terminology (indicate a diagnosis or syndrome instead of symptoms).

Date of onset and date of resolution (i.e. actual dates when the event starts and is resolved rather than dates when the Investigator is informed).

- Severity.
- Relationship to IMP.
- Relationship to study procedure.
- Outcome.
- Seriousness.
- Action taken regarding the IMP.
- Any action taken regarding the event, whether by the Investigator, the subject (as reported by the subject), or by another physician (as reported by the subject or in the subject's medical record).

AEs requiring therapy must be treated with recognized standards of medical care to protect the health and well-being of the subject. Any treatment given will be reported on the page "Concomitant medication" of the CRF.

9.1.1.1 Assessment of Severity

The severity of the clinical AE is graded according to the Common Terminology Criteria for Adverse Events (CTCAE) version 4.0. The CTCAE scale will be provided to the Investigators.

Should an event be missing in one of the scales, the following 3 point scale is used:

- Mild: Discomfort noticed, but no disruption of normal daily activity.
- Moderate: Discomfort sufficient to affect normal daily activity.
- Severe: Inability to work or perform normal daily activity.

The correspondence between the two scales is as follows:

CTCAE	3-Point Scale
1	Mild
2	Moderate
3/4/5	Severe

9.1.1.2 Relationship to IMP and/or Procedures

The relationship of each AE to IMP and/or study procedures will be evaluated as follows:

- Unrelated: There is evidence of relationship to a cause other than the IMP/procedure. Does not meet criteria listed under unlikely, possible or probable.
- Unlikely: Does not follow a reasonable temporal sequence from administration. Is most likely produced by the subject's clinical state or by environmental factors or other therapies administered.
- Possible: Follows a reasonable temporal sequence from administration. Is not likely produced by the subject's clinical state or by environmental factors or other therapies administered.
- Probable: Follows a reasonable temporal sequence from administration. Clear-cut temporal association with IMP.

9.1.1.3 Outcome

The outcome of each AE will be rated as follows:

- Recovered.
- Not recovered.
- Recovered with sequelae.
- Fatal. This outcome is to be used only for the event leading to death. The outcome of all other events at the time of the death must be reported. The outcome of ongoing ones is reported as "not recovered".
- Unknown.
- Worsening. This outcome is used when an AE worsens. The new status of the event is documented as another AE on the AE page in the CRF.

9.1.2 Documentation

AEs will be reported in the source document with at least the nature, the start date and the treatment (if applicable) of the event.

9.2 Ocular Inflammation

Specific assessment and documentation of ocular inflammation will be required. Ocular inflammation is an expected event based on preclinical NHP studies of GS010 and Phase I evaluation of GS010 in GS-LHON-CLIN-01. Specific, standardized schemes for assessing anatomic location, severity and clinical evolution will be employed. Specific scales will be used for anterior uveitis (anterior chamber) and intermediate uveitis (vitreous).

The Standardization of Uveitis Nomenclature (SUN) Working Group provided standardized methods for (1) anatomic classification of uveitis; (2) grading scheme for anterior chamber cells; (3) grading scheme for anterior chamber flare; and (4) activity of

uveitis terminology (for clinical evolution) (Jabs 2005). Investigators will grade cases of ocular inflammation according to these scales. These scales are provided in Table 1, Table 2, Table 3, Table 4, and Table 5 below.

Table 1 Anatomic Classification of Uveitis (SUN Working Group)

Туре	Primary Site of Inflammation ^a	Includes
Anterior uveitis	Anterior chamber	Iritis
		Iridocyclitis
		Anterior cyclitis
Intermediate uveitis	Vitreous	Pars planitis
		Posterior cyclitis
		Hyalitis
Posterior uveitis	Retina or choroid	Focal, multifocal, or diffuse choroiditis
		Chorioretinitis
		Retinochoroiditis
		Retinitis
		Neuroretinitis
Panuveitis	Anterior chamber, vitreous, and retina or choroid	

SUN = Standardization of Uveitis Nomenclature

Table 2 Grading Scheme for Anterior Chamber Cells (SUN Working Group)

Grade	Cells in Fluid ^a
0	<1
0.5+	1-5
1+	6-15
2+	16-25
3+	26-50
4+	>50

SUN = Standardization of Uveitis Nomenclature

^a As determined clinically. Adapted from the International Uveitis Study group anatomic classification.

^a Field size is a 1 mm by 1 mm slit beam.

Table 3 Grading Scheme for Anterior Chamber Flare (SUN Working Group)

Grade	Description
0	None
1+	Faint
2+	Moderate (iris and lens details clear)
3+	Marked (iris and lens details hazy)
4+	Intense (fibrin or plastic aqueous)

SUN = Standardization of Uveitis Nomenclature

Table 4 Activity of Uveitis Terminology (SUN Working Group)

Term	Definition
Inactive	Grade 0 cells ^a
Worsening Activity	Two step increase in level of inflammation (e.g., anterior chamber cells, vitreous haze) or increase from Grade 3+ to Grade 4+.
Improved Activity	Two step decrease in level of inflammation (e.g., anterior chamber cells, vitreous haze) or decrease to Grade 0.
Remission	Inactive disease for ≥ 3months after discontinuing treatments for eye disease

SUN = Standardization of Uveitis Nomenclature

Grading of vitreous cells will be performed based on the slit lamp examination utilizing a 1 mm by 1 mm slit lamp beam and the same grading scheme utilized for anterior chamber cells (Table 2).

Grading of vitreous haze will be performed in a standardized fashion by the central ophthalmology reading center, based on color fundus photos of the posterior pole. Baseline color fundus photos will be obtained at Visit 1 for all subjects. Color fundus photos will be obtained at subsequent visits when needed for grading of vitreous inflammation. The National Institutes of Health grading system (Nussenblatt 1985) will be used to grade the vitreous haze on the fundus photo. Table 5 and photos will serve as the basis for vitreous haze grading:

^a Applies to anterior chamber inflammation.

Table 5 National Institutes of Health Grading System for Vitreous Haze

Grade	Amount of Vitreous Flare/Haze
0	No flare
0.5+	Trace
1+	Clear optic disc and vessels, hazy nerve fiber layer
2+	Hazy optic disk and vessels
3+	Optic disc visible
4+	Optic disc not visible
Quality Unsatisfactory	Photo quality inadequate for vitreous inflammation grading
Not Performed	Photograph not performed

9.3 Clinical Laboratory Changes

A laboratory abnormality is reported as an AE if it is out of range, considered by the Investigator as clinically significant (i.e. with clinical manifestations or requiring treatment or clinical management) and confirmed by a repeat measurement (if relevant). Worsening of laboratory parameters from pre-drug administration state will be considered on the same basis.

9.4 Concomitant Medication Assessments

The Investigator or designee will record any concomitant therapies given for the treatment of AEs on the concomitant medication page of the subject's source document and CRF. During the study, any medication taken by the subject is to be reported by the subject and noted on the subject's source document and CRF. Any changes in concomitant therapy during the study will be documented, including cessation of therapy, initiation of therapy, and dose changes.

9.5 Adverse Event Follow-up

AEs occurring during the course of the study must be followed until resolution or the last visit planned by the protocol. AEs not resolved by the last visit planned by the protocol will be listed in the CRF as continuing/not resolved.

Subjects who experience the onset of an AE thought to be related to IMP after their final visit (Visit 12 or the end of study visit) will be followed up until the resolution of the AE or for 30 days after the AE occurs, whichever comes first. AEs not resolved after 30 days will be listed in the CRF as continuing/not resolved. SAEs thought to be related to IMP occurring after the final visit (Visit 12 or the end of study visit) must be reported as described in Section 10.3.

9.6 Pregnancy

If a female subject or the partner of a male subject believes she is pregnant (e.g., missed period, self-administered pregnancy test) the subject will be instructed to return to the clinical unit within 48 hours to undergo a serum pregnancy test. All confirmed pregnancies that occur within this study will be followed until resolution (i.e., termination [voluntary or spontaneous] or birth).

If the pregnancy is confirmed before the subject receives IMP, the subject will be excluded from study participation and will not receive IMP.

Pregnancy (without associated unexpected or adverse sequelae) is not a reportable AE but must be reported to the Sponsor within 24 hours of the Investigator or study staff first becoming aware of the subject's condition.

10 SERIOUS ADVERSE EVENTS

10.1 Definition of Serious Adverse Event

A SAE is any AE that meets any of the following criteria:

- Results in Death.
- Is Life-threatening.
- Requires Inpatient hospitalization or prolongation of existing hospitalization.
- Results in Persistent or significant disability/incapacity.
- Is a Congenital anomaly/birth defect in the offspring of a subject who received IMP.

Other important medical events that may not result in death, be life-threatening, or require hospitalization, may be considered an SAE when, based upon appropriate medical judgment, they may jeopardize the subject and may require medical or surgical intervention to prevent one of the outcomes listed in this definition. Examples of such events are:

- Intensive treatment in an emergency room or at home for allergic bronchospasm.
- Blood dyscrasias.
- Convulsions that do not result in inpatient hospitalization.

10.2 Definition of Terms

Life threatening: An AE is life threatening if the subject was at immediate risk of death from the event as it occurred; i.e., it does not include a reaction that if it had occurred in a more serious form might have caused death. For example, drug induced hepatitis that resolved without evidence of hepatic failure would not be considered life threatening even though drug induced hepatitis can be fatal.

Hospitalization: AEs requiring hospitalization should be considered SAEs. Hospitalization for elective surgery for a pre-existing condition that has not worsened or hospitalization for routine clinical procedures that are not the result of an AE need not be considered AEs or SAEs. If anything untoward is reported during the procedure, that occurrence must be reported as an AE, either 'serious' or 'non-serious' according to the usual criteria.

In general, hospitalization signifies that the subject has been detained (usually involving at least an overnight stay) at the hospital or emergency ward for observation and/or treatment that would not have been appropriate in the physician's office or outpatient setting. When in doubt as to whether 'hospitalization' occurred or was necessary, the AE should be considered serious.

Disability/incapacitating: An AE is incapacitating or disabling if the experience results in a substantial and/or permanent disruption of the subject's ability to carry out normal life functions.

10.3 Reporting Serious Adverse Events

Any SAE occurring during the course of a study, i.e. between signature of the ICF and the end-of-study visit, irrespective of the treatment received by the subject MUST be reported to the Sponsor or their representative. The Investigator must complete and fax a "Serious Adverse Event Form" to the Sponsor or their designee within 24 HOURS of occurrence or knowledge of the event.

An Investigator's delegate may complete the SAE form; however, the Principal Investigator or delegate physician must sign it. The form can be sent to the Sponsor or their designee with the delegate's signature if the Principal Investigator/delegate physician's signature cannot be obtained within one working day. The Principal Investigator/delegate physician's signature must be obtained as soon as possible, as must his/her evaluation of the relationship to the IMP. The signed form must be faxed to the Sponsor or their designee immediately.

The SAE form must be completed in English.

10.3.1 Follow-up

If follow-up information is not available at the time of the event, this information must be forwarded to the Sponsor or their designee within one day of knowledge. The Sponsor or their designee may request information as needed.

10.3.2 Post-Study Serious Adverse Events

Any SAE occurring after the end of study visit and that is considered by the Investigator to be possibly or probably related to the IMP must be reported to the Sponsor or their designee as described above.

If the end of study visit is performed less than 28 days after IVT injection, ALL SAEs occurring between the end of study visit until 28 days after IVT injection will be reported to the Sponsor or their designee, regardless of their relationship to the IMP.

10.3.3 Notification to Regulatory Authorities/Gene Therapy Bodies/IRBs/IECs

The Sponsor or their designee is responsible for notifying serious and unexpected AEs to Health Authorities and to IRBs/IECs in accordance with local law.

Gene Therapy Bodies will be informed as locally required.

10.3.4 Information to Investigator

When an SAE has been reported to Health Authorities, the Sponsor or their designee will inform all other Investigators working in this study as well as those working with GS010 in other studies in accordance with local laws and regulations.

10.3.5 Documentation

All SAEs will be reported on the AE pages of the CRF using the same information as documented on the SAE form and in source documents. Copies of SAE forms will be filed in the Investigator Site File along with copies of any correspondence with the IRB/IEC. The Investigator Site File will also include copies of notification letters and/or faxes of forms sent to Health Authorities and Gene Therapy Bodies if appropriate.

11 QUALITY CONTROL AND ASSURANCE

11.1 Quality Control

Steps to be taken to ensure the accuracy and reliability of data include the selection of qualified Investigators and appropriate study centers, review of protocol procedures with the Investigators and associated personnel before the study, and periodic monitoring visits by the Sponsor or their designee. Written instructions will be provided for study drug preparation and dosing, and collection, preparation, and shipment of blood samples. Guidelines for CRF completion will be provided and reviewed with study personnel before the start of the study. The Sponsor (or designee) will review CRFs for accuracy and completeness during on-site monitoring visits and after transmission to the Sponsor (or designee). Any discrepancies will be resolved with the Investigator or suitably qualified designee, as appropriate.

11.2 Quality Assurance

This study will be organized, performed, and reported in compliance with the protocol, standard operating procedures (SOPs), working practice documents, and applicable regulations and guidelines.

In accordance with the standards defined in Sponsor SOPs and applicable regulatory requirements, clinical studies sponsored by the Sponsor are subject to Sponsor Quality Audits at the study sites, which will be conducted by personnel from an appropriate unit. Site visit audits will be made periodically by the Sponsor's (or the CRO's) qualified compliance auditing team, which is an independent function from the study conduct team. Audits will include, but are not limited to, review of drug supply, presence of required documents, the informed consent process, and comparison of CRFs with source documents. The Investigator agrees to participate with audits conducted at a reasonable time in a reasonable manner. Full consultation with the Investigator will be made prior to and during such an audit, which will be conducted according to the Quality Assurance Unit SOPs. In addition, this study is subject to audit by regulatory authorities. If such a regulatory inspection occurs, the Investigator agrees to allow the regulatory inspector direct access to all relevant study documents. The Investigator should contact the Sponsor immediately if this occurs and must fully cooperate with the inspection conducted at a reasonable time in a reasonable manner.

12 STATISTICS

12.1 General Considerations

A statistical analysis plan (SAP) will be prepared after the protocol is approved and before database lock occurs. The SAP will provide further details regarding the endpoints, data handling rules, and the statistical methodology to be used to address all study objectives. The SAP will also include formats for the summary and analysis tables, listings, and graphical displays.

GS-LHON-CLIN-03A (RESCUE) will include subjects affected for 180 days or less. Evidence indicates that improvement due to gene transfer therapy may be greatest at earlier stages of disease. This trial randomizes the right eye of each subject to receive GS010 or sham treatment in a 1:1 ratio and also uses the Efron's minimization method to balance as best as possible the treatment allocation to better- and worse-seeing eyes, as described in Section 8.6 for secondary analysis.

Data for quantitative variables will be presented by arithmetic mean (for other continuous variables), standard deviation (SD) median, first quartile (Q1), third quartile (Q3), minimum and maximum. Data for binary variables (responder analysis) will be presented by using counts and percentages. Least square (LS) means, 95% confidence interval and P-values will be reported derived from models and statistical tests.

12.2 Sample Size

Sample size calculation is based on the primary endpoint (LogMAR) and on the paired comparison of treated and sham eye. There is no published data regarding the within subject variance and the sample size calculation through paired comparison will therefore be very speculative for two reasons. The first reason is the within subject correlation between right and left eye and the second reason is the absence of information on the within and between subject variance of the LogMAR. Usually the within subject correlation is positive and the use of a null correlation is conservative. The absence of information on the LogMAR requires a second rough approximation of the mean and variance of LogMAR because the mean of ETDRS (Lam et al. 2014) is highly correlated to the variance of ETDRS ($R^2 = 0.839$ for the log-log relationship). This correlation is in favor of the use of the LogMAR to stabilize the variance but the transformation from ETDRS mean and variance to LogMAR mean and variance requires additional assumptions. Starting with a mean 23.4 and a standard deviation of 28.3 (Lam et al. 2014) and a difference of 20 letters on average between treated and sham eye, using the relationship between the log mean and the log variance obtained with Lam et al. (2014) results (log variance = 1.743 log mean + 0.48, $R^2 = 0.839$) and assuming a perfect lognormal distribution of ETDRS, the difference in means of the lognormal distributions is 0.65 (3.32 - 2.67) and the pooled standard deviation of the log distributions is 0.914. Assuming no correlation between both eyes, the within subject standard deviation is $(2x0.914^2)^{0.5} = 1.29$. The standardized difference in means is therefore 0.65/1.29 = 0.504 rounded to 0.50. The sample size required to get a power of 85% is exactly 36 subjects.

12.3 Analysis Populations

12.3.1 Intent-to-Treat Population

The intent-to-treat population will consist of all subjects who are randomized and receive study treatment (GS010 or sham treatment). This population will be the population for the primary efficacy analysis.

12.3.2 Safety Population

The safety population is defined as those subjects who received IMP. This population will be used as the population for all safety analyses.

12.4 Statistical Methods

12.4.1 Primary Analysis and Associated Planned Analyses

The primary analysis will be performed on the ITT subject population, which consists of all randomized and treated subjects. The change from baseline to Week 48 in the LogMAR acuity will be the primary response. The ETDRS score will not be directly used because there is a clear relationship between the mean and variance and according to Taylor's power law ($\log SD^2 = 1.743 \log mean + 0.48$, $R^2 = 0.839$) the best transformation is the logarithm (slope close to 2 and ease of interpretation of the difference in means of log). Because LogMAR is a logarithmic scale and is well known by ophthalmologists, this scale is retained as the primary one. The change from baseline of the treated eye will be compared to the change from baseline of the sham eye using a mixed model including the subject, the treatment and the baseline as covariates.

The center will not be included in the analysis as the number of subjects recruited per site will be very small. The difference in the mean change from baseline to Week 48 between the two treatment groups and associated 95% confidence interval will be reported. Alternative non parametric analysis (signed Wilcoxon test) will be performed as a sensitivity analysis to decrease the influence of possible outliers.

The treatment effect reflects well the effect on the better- and worse-seeing eye if no marked interaction between the eye status (better- versus worse-seeing) and treatment exists. To verify this hypothesis, a model including the subject as a random factor, the treatment as a fixed factor as well as the eye status (better- or worse-seeing) and the interaction between eye status and treatment will be fitted. If the P-value of the interaction test is below 0.15 a potential interaction is detected. In that case the better-seeing eye treated with GS010 will be compared to the better-seeing eye treated with sham and the worse-seeing eye treated with GS010 will be compared the worse-seeing eye treated with sham in an ANCOVA model including the LogMAR at baseline and the treatment. The study is then powered $(1-\beta=0.8)$ to detect a difference of approximately 30 letters between the two treatments.

A meta-analysis combining study GS-LHON-CLIN-03A (RESCUE) and study GS-LHON-CLIN-03B (REVERSE) is planned to verify whether the treatment effect at Week 48 as well as at Week 96 is dependent upon the time from onset of disease. If the treatment effect does not depend upon the eye status, a model using the change from baseline as the response, the subject as a random factor, the treatment as a fixed factor, the time from the onset of disease as a covariate and the interaction between the treatment and the time from the onset will be fitted. If the treatment effect is not the same in the better-and worse-seeing eye, a model will be fitted for the better-seeing eye and another model will be fitted for the worse-seeing eye. The subject factor will not be included in the model, but the LogMAR at baseline, the treatment, and the time from onset of disease will be included.

The generalizability of the treatment effect across countries will be addressed in the metaanalysis because the number of subjects per country could be sufficient to detect major heterogeneity.

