#### Primary Analysis for EMA

The null and alternative hypotheses for the primary endpoint are defined below

$$H_0: \mu_{\text{All-GS010}} = \mu_{\text{All-Sham}}$$

$$H_1: \mu_{\text{All-GS010}} \neq \mu_{\text{All-Sham}}$$

Where  $\mu$  presents the mean change from baseline to Week 48 in LogMAR. “All” represents all eyes treated with GS010 or Sham

The primary analysis will be performed on the ITT population. The change from baseline to Week 48 in the LogMAR acuity will be the primary response. The change from baseline of all-GS010 eyes will be compared to the change from baseline of all-Sham eyes (intra-subject comparison) using a mixed model of analysis of covariance (ANCOVA) using the following terms (or covariate) in the model:

- Subject as random factor
- Eyes of the subject as random factor,
- Treatment and the
- Baseline LogMAR for each eye.

The analysis will be performed based on alpha of 0.05. The statistical significance in favor of GS010 against sham will provide evidence of the advantage of using GS010 for halting visual acuity loss or improving visual acuity in subjects with LHON with duration of vision loss of 6 months or less. The difference in the mean change from baseline (adjusted mean difference) to Week 48 between the two treatment groups and associated 95% confidence interval will be reported.

The center will not be included in the analysis as the number of subjects recruited per site will be very small. However, stratification by geographical area will be performed as a sensitivity analysis. Neighboring countries can be pooled together to reach at least 9 subjects per geographical entity. The pooling will be performed during the masked review of data.

All the model diagnostics will be checked.

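### The first-branch pooled RESCUE + REVERSE model and the Week 48 eye-status interaction model omit baseline LogMAR, which costs precision if baseline predicts change

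*Protocol*

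**What the plan says.** Protocol 12.4.1 describes five models for the change in LogMAR. Three name baseline and two do not.

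| Model | Terms listed | Baseline LogMAR |
|---|---|---|
| Primary, Week 48 | "a mixed model including the subject, the treatment and the baseline as covariates" | yes |
| Eye-status interaction | "a model including the subject as a random factor, the treatment as a fixed factor as well as the eye status", and the eye status by treatment interaction | no |
| Follow-on comparison within better-seeing and within worse-seeing eyes | "in an ANCOVA model including the LogMAR at baseline and the treatment" | yes |
| Pooled, effect does not depend on eye status (first branch) | "a model using the change from baseline as the response, the subject as a random factor, the treatment as a fixed factor", time from onset, treatment by time | no |
| Pooled, effect depends on eye status (second branch) | "The subject factor will not be included in the model, but the LogMAR at baseline, the treatment, and the time from onset" | yes |

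The eye-status model carries a decision rule: "If the P-value of the interaction test is below 0.15 a potential interaction is detected".

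The SAP's primary model for EMA also includes "Baseline LogMAR for each eye". The SAP's visible text restates neither the pooled model nor the 0.15 rule. It does test eye status by treatment in the repeated-measures model under Time Course of the response (section 9.5.5), with baseline among the covariates, and it reports that interaction's p-value.

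**The concern.** The protocol gives no reason for dropping baseline from these two models. In the first pooled branch the quantity of interest is how the GS010-minus-sham difference in change varies with time from onset. The protocol describes vision loss as typically bilateral and sequential, with a median delay of 2 months, and it admits subjects with only one eye affected. The two eyes can therefore differ at entry. If change depends on baseline, that gap enters the between-eye difference as noise that the model could have removed.

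Dependence on time from onset is the stated purpose of the pooled analysis, and protocol 12.1 says that benefit may be greatest in earlier disease. A wider interval on that slope makes the question harder to answer. The eye-status test has the same weakness, and in the protocol it decides whether the better-seeing and worse-seeing eyes are analysed separately.

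**Working it through.** **1. The plan's own figures.** Protocol 12.2 uses a standardised paired difference of 0.50: n = ((1.960 + 1.036)/0.50)² = 35.9, so 36. Power at 36 is 85.1% by the normal approximation and 83.1% by noncentral t, against a stated 85%. SAP 3.3 uses 0.3/0.594 = 0.505 with 36 subjects: 83.8% by t and 85.8% by the normal approximation, against a stated 84%. These figures reproduce and do not involve the two models at issue. The documents give no power or precision for either interaction test.

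**2. What the first-branch slope is made of.** Each subject has one GS010 eye and one sham eye. With time from onset taken at subject level, the treatment by time term is the slope on time of D, the change in the GS010 eye minus the change in the sham eye. The random subject effect is common to both eyes and cancels from D. The baseline gap G between the eyes does not cancel. If change varies with baseline at slope b, D contains b × G, up to sign.

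**3. Size for the pooled model.** Inputs:
- SD(D) = 0.594, unadjusted, from SAP 3.3 (a Phase I/II figure, applied here to both trials).
- b = 0.3 to 0.6, assumed.
- SD(G) = 0.4 to 0.6 LogMAR, assumed.

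Variance left after adjustment = 0.594² − b² × SD(G)², with 0.594² = 0.3528. The unadjusted standard error exceeds the adjusted one by the factor √[0.3528 / (0.3528 − b² × SD(G)²)].

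| b | SD(G) | b² × SD(G)² | Variance left | SE factor |
|---|---|---|---|---|
| 0.3 | 0.4 | 0.0144 | 0.3384 | 1.02 |
| 0.45 | 0.6 | 0.0729 | 0.2799 | 1.12 |
| 0.6 | 0.6 | 0.1296 | 0.2232 | 1.26 |

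The implied correlation of D with G is b × SD(G)/0.594, which is 0.20, 0.45 and 0.61 in the three rows.

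**4. Cost if baseline is not prognostic.** Adding one covariate multiplies the standard error by about √(1 + 1/df). For 72 subjects (df about 69) this is √(1 + 1/69) = 1.007. For 36 subjects (df about 33) it is √(1 + 1/33) = 1.015.

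**5. Check by simulation.** Random-intercept REML models were fitted with and without baseline, 1,500 runs per setting, 72 subjects. At eye-level baseline-change correlations of about 0, −0.29, −0.52 and −0.67, the mean standard error with baseline was 1.00, 0.98, 0.91 and 0.82 times that without. The direction and order of size agree with step 3.

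**6. The eye-status model.** A subject's better-seeing eye is treated or the worse-seeing eye is. The interaction therefore compares the two-eye sum of change between those two groups, about 18 subjects each. It is a between-subject contrast, so the random subject term does not remove variation in subjects' overall baseline level. The minimisation in protocol 8.6 balances which eye is treated, not that level. With ρ the correlation of baseline with change for this contrast, the standard error with baseline relative to without is about √[(1 − ρ²)(1 + 1/33)]: 1.015 at ρ = 0, 0.97 at 0.3, 0.88 at 0.5. The documents do not give ρ.

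**The case against.** The strongest reply concerns the eye-status model. Protocol 12.1 leaves methodological detail to the SAP. The SAP runs the best-eye and worst-eye ANCOVAs unconditionally, each with baseline, and its stated LogMAR test of eye status by treatment already adjusts for baseline. A reader might infer that the operative within-trial plan tests eye status without baseline; the visible SAP does not support that. What remains is narrower. The SAP's interaction is averaged over visits and carries no 0.15 rule, so it is not the protocol's Week 48 test, and the choice of pooled branch could still rest on that test.

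Three other stronger readings are tempting, and none is supported:

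- **That both tests certainly lose precision.** This needs a baseline-change relationship, which the documents do not give. The loss could be close to zero.
- **That the lost precision sits mostly in early subjects.** No document gives the between-eye gap by time from onset, and step 3 uses a single gap SD for everyone.
- **That both pooled branches need a study term.** In the first branch as written, with both eyes observed, a study main effect is constant within subject and cancels from both the treatment contrast and the treatment by time slope. It is relevant only to the second branch, which drops the subject factor and compares between subjects.

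It is also fair to say that SAP 9.5.3 spends all type I error on the primary endpoint and treats other analyses as supportive. Parts of the SAP are redacted, so the final pooled model may be specified where it cannot be seen. No document says that the pooled treatment effect will be set against the primary estimate.

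**Conclusion.** The omission is real in the protocol text, and nothing visible in the SAP corrects it for the pooled model. If baseline predicts change, the first-branch treatment by time slope is estimated with a standard error about 2% to 26% larger than necessary. That range rests on 0.594 holding in both trials, on time from onset taken at subject level, and on the assumed b and SD(G). If baseline is not prognostic, adjusting costs about 1%. Since the sponsor adjusts for baseline in the primary model, omitting it here has little to recommend it.

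For the eye-status model the point is mainly one of aligning the protocol with the SAP. No percentage loss for it can be tied to the documents' figures.

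The primary analysis, the sample size of 36 and the stated power do not change. This is a low-severity improvement.

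**What to change.** Add each eye's baseline LogMAR to the first-branch pooled model in protocol 12.4.1, or state why it is left out. Add it also to the Week 48 eye-status interaction model, so that it matches the baseline-adjusted model in SAP 9.5.5. If a study fixed effect is wanted, add it to the second pooled branch, where the comparison is between subjects.

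The covariate is already collected, so the cost is wording only. Make the change before the Week 48 unmasking: protocol Appendix V rules out SAP amendments once the randomisation code is broken and treats later additions as ad hoc.
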